#### 7.4.2 Concomitant Medication and/or Treatments

##### 7.4.2.1 Permitted concomitant medications during the study:

- Antipyretics except NSAID
- Systemic and/or local mucolytics

***Strictly Confidential***

- Local decongestants (to be taken away from nasal score assessment, 2 hours minimum)
- Systemic antihistamines only if taken for more than 4 weeks at screening
- Antitussive
- Antibiotics

#### ***7.4.2.2 Non-permitted concomitant medications:***

- Local or systemic corticosteroids
- NSAID
- Saline nasal spray

#### **7.4.3 Activities performed by sponsor representatives (excluding monitoring)**

The sponsor has delegated to the CRO the provision of tasks relative to the project management, medical writing, clinical operations, data management and statistics, and site(s) oversight. These delegated tasks have been established through a Study Management Plan, signed by both parties.

The CRO will rely on its in-force Quality Management System to ensure that the clinical investigation is conducted and monitored, and that data are generated, documented, recorded, evaluated and reported in compliance with the ISO 14155:2020, the CIP, any subsequent amendment(s) and any other applicable standards and in accordance with the regulation requirements. The CRO will ensure the management of ongoing risk in close collaboration with the sponsor throughout the clinical investigation and will take all measures to protect rights, safety and well-being of patients who participate in the study.

Tasks still under sponsor responsibility:

- Reporting of non-compliance trends and safety issues to the Ethics Committee/Competent Authorities and investigators.
- Triggering audit to be performed if applicable.

#### **7.4.4 Any known/foreseeable factors that can compromise the outcome of the clinical investigation and methods for addressing these factors**

There is no known/foreseeable factor that can compromise the outcome of the clinical investigation.

#### **7.4.5 Follow-up and medical care after completion of the study**

The patients will receive all treatments needed if the common cold is not cured or in case of complication or safety issues. In this case, the patient will be followed until the end of the issue.

#### **7.4.6 Potential use of samples obtained from subjects**

Not applicable.

## 7.5 Monitoring plan

A risk-based monitoring plan included in a separate document will describe in detail who will conduct the monitoring, at what frequency monitoring will be done, at what level of detail monitoring will be performed, and the distribution of monitoring reports. Results of the risk assessment will be used to develop a risk-based monitoring plan and a supporting rationale.

### 7.5.1 Initiation visit

The study will only start at a site after:

- The Ethics Committee has granted approval and the Competent Authority has been notified for the conduct of the study,
- Essential documents are in place, such as CVs of the Investigators and site staff, and the Clinical Trial Agreement signed.

In agreeing to participate, the investigator undertakes to strictly comply with the study protocol, Good Clinical Practice, the Bulgarian regulation and to MDR. The investigator also guarantees the authenticity of the data collected in the context of the study and agrees to the legal provisions for study sponsor quality control.

### 7.5.2 Monitoring

Study monitoring delegated by Lallemand Pharma AG to the CRO will be performed at various stages of the study. Monitoring will include on-site visits and centralized data review to ensure that the investigation is conducted according to the CIP and comply with applicable regulations and deadlines. On-site review of electronic Case Report Form (e-CRFs) will include the review of forms for completeness, clarity, and consistency with source documents available for each subject. In case of queries, the investigator should respond within agreed timelines.

The investigator must permit study-related monitoring visits, audits review by the Ethics Committee, and allow direct access to source data and source documents provided that subject confidentiality is protected. In case of an audit appointed by Lallemand Pharma, the investigator will receive written notification in advance.

### 7.5.3 Routine Close-out

Routine close-out procedures will be conducted ensuring that the PIs records are complete, all documents needed for the sponsor files are retrieved, remaining clinical investigation materials are disposed of, previously identified issues have been resolved.

### 7.5.4 Retention of Documentation

The Principal Investigator will retain all copies of the records for a period of 10 years from the completion of the clinical investigation. In any circumstances, the PI must contact the sponsor prior to disposing of any records related to the clinical investigation. Should the data be no longer required for regulatory purposes then the confidential destruction of said documents will be approved. Should the

data be maintained for longer, Lallemand Pharma AG will make this information available to all appropriate bodies in the same way. A list of essential documents to be maintained will be provided to each site at initiation.

Should the PI have to move/retire, or otherwise leaves his/her position, he/she will provide Lallemand Pharma AG with the name and address of the person assuming responsibility for records relating to this clinical investigation.

## **8. Statistical design and analysis**

The statistical analysis will be detailed in the Statistical Analysis Plan. This section provides a summary.

### **8.1 Analysis population**

The safety population consists in all the patients included in this study who will have taken at least one puff of the nasal spray.

Full Analysis Set (FAS): all subjects who will have taken at least one puff of nasal spray and with at least one post-baseline efficacy data.

Safety endpoint will be performed on safety population.

The analysis of primary and secondary endpoints will be performed on the FAS population.

### **8.2 Baseline Characteristics**

Continuous variables will be summarized using the mean, standard deviation, median, minimum, maximum and quartiles. Categorical variables will be summarized using frequency counts and percentages.

All statistical tests will be 1-sided and performed using a 0.05 significance level.

### **8.3 Primary endpoint**

For the primary criterion analysis, AUC for the WURSS-21 will be compared between Healsea® Rescue\* group and Placebo group using a Student's t-test. If the usual applicability assumptions for the Student's t-test are not met, a Mann-Whitney test will be used.

### **8.4 Secondary endpoints**

-The analysis of the primary endpoint will be completed by an analysis of the AUC for each of the WURSS-21 components (symptoms and Quality-of-Life).

-Duration endpoints will be summarized using the medians, with 95% CIs for the medians by group. Results for Healsea® Rescue\* group and Placebo group will be compared using Wilcoxon-Mann-Whitney test.

-The number of days of use of concomitant treatments in each group will be compared by means of chi-square test or exact Fisher test.

-The subject general satisfaction in each group will be compared by means of chi-square test. And the global subject feedback on treatment use in each group will be compared by means of exact Fisher test.

**-Safety:**

All adverse events/incidents/expected side effects will be listed, but only treatment-emergent adverse events/incidents (non-serious + serious) will be summarized.

Adverse events/incidents/expected side effects will be summarized by the number and percentage of patients (by treatment group), classified by System Organ Class and Preferred Term as defined by MedDRA dictionary.

For a given treatment group, a given adverse event will be counted treatment emergent only once per patient during the treatment period.

Frequency and percentage of patients with at least one reported adverse event/ incident / expected side effects will be tabulated by System Organ Class and by treatment group.

## **8.5 Sample Size calculation and justification**

A sample of **180** subjects (90 subjects per group) will be needed to provide 80% power with a 1-sided test at a 0.05 significance level to detect a difference between Healsea® Rescue\* and Placebo groups AUC of 30% [12].

Assuming that approximately 10% of subjects may drop-out the study, **200** subjects will be randomly assigned at a ratio 1:1 to Healsea® Rescue\* and Placebo (100 subjects per group).

## **8.6 Rationale for the number of procedures to be performed by a single user**

Only non-burdensome and non-invasive procedures are planned in the study investigation, such as quality of life or satisfaction questionnaires. Two visits are scheduled to assess the study criteria. The phone call is performed to ensure that the patient has stopped the treatment after 14 continuous intakes.

## **8.7 Interim analysis**

Not applicable.

*Strictly Confidential*

## **8.8 Management of bias (randomization, blinding)**

See section 7.1.2

## **8.9 Management, justification, and documentation of missing data, including drop-outs**

Missing data for the primary endpoint (WURSS-21) will be estimated by interpolation.

## **8.10 Procedures for reporting any deviation(s) from the original statistical analysis plan**

Any deviation(s) from the original statistical analysis plan will be reported in the statistical analysis plan and in the clinical investigation report.

## 9. Data Management

Subject data will be entered into an electronic case report form.

### 9.1 Source documents

The source documents (e.g., medical file, clinical and office charts, log for compliance data...) which contain the source of data recorded in the CRF should be specified. The e-diary will be used as source document for WURSS-21, concomitant treatments and adverse events/incidents reported by patient.

Each subject will be assigned and identified by a unique screening number. Any reference made to an individual subject within the study must be done using the unique screening number.

### 9.2 Methods for data entry and collection

A validated electronic case report form (eCRF, 21 CFR Part 11 compliant) will be used to collect clinical data for this study. Some of the study data will be recorded in a validated and GCP/GDPR compliant e-diary by the patient after secure logging to the study website and will be automatically uploaded in the e-CRF:

- WURSS-21,
- Adverse event/incidents/expected side effects and concomitant treatments,

Lallemand Pharma is responsible for designing the e-CRF. eCRF training will be given to appropriate personnel before/at initiation of the investigation site. Patients will be instructed how to connect to the e-diary at visit 1.

### 9.3 Procedure used for CRF tracking, data review, database cleaning and issuing/resolving data queries.

The Data Management process includes all activities related to data handling regarding:

- Set-up of eCRF and database
- Specification of on-line checks
- Data entry/Data editing
- Export of data from e-CRF to SAS
- Creation of post-entry checks and listings
- Clean-file process including execution of post-entry checks and listings
- Post clean-file tasks

Data entry will be done by investigators and other authorized personnel at the site(s). When entering data, on-line checks are encoded in the e-CRF for consistency and validation. Whenever required, queries issued from this review will be submitted to the investigator for resolution and then tracked until corrections are entered and validated.

A data blind review meeting will be held prior to database lock.

The review process prepared by the project manager, data manager, study monitor, medical manager and statistician will be attended by at least the following:

- Coordinating investigator,
- Study monitor,
- Sponsor Vigilance representative,
- Project managers from the sponsor and from the CRO,
- Data manager,
- Statistician.

The review is also required for defining the analysis populations and validating the statistical analysis plan.

The meeting will be documented by written and signed minutes that will act as the basis for data processing by the Biometrics Department.

All decisions on the evaluability of the data from each individual subject for the statistical analysis must be made and documented before locking the database.

Data will be retained for at least 10 years after investigation closure. All data collected in the electronic Case Report Forms will be handled and archived under the responsibility Lallemand Pharma.

## **9.4 Procedures for verification, validation and securing of electronic clinical data system**

The EXAGIS software is installed on a Linux server (secure Data Center) hosted at the OVH company that guarantees the security, maintenance, as well as regular antivirus and firewall updates of this dedicated server. Any modification to the data is tracked, i.e. creation and changes are timestamped and authors are recorded. Software access is restricted to authorized users using individual encrypted passwords. Data processing via SAS software (SAS Institute, Cary, NC, USA) is carried out on a Windows 2012 R2 production server at OVH, using direct access by SAS or MySQL Workbench.

## **9.5 Procedures to maintain and protect subject privacy**

It is the responsibility of the sponsor to maintain a security system that prevents unauthorized access to the data, both internally and externally.

Subject privacy is protected through the EXAGIS system at different levels to preclude unauthorized access to data:

- Only authorized persons can access the data:

Access to the database is restricted to authorized users using individual encrypted passwords. For all co-workers (from remote or on-site), an identification via a VPN is mandatory. Then, access to each server is always done through an authentication with a login and a personal password.

- The risk of data breaches:

The risk is minimized by full encryption and controlled access.

- External/internal interactions are actively protected:

A standard operating procedure (SOP) details all processes implemented for ensuring network security. This SOP mentioned the following subjects: system update, antivirus, antimalware, VPN management, user access accounts, password policy, training and awareness of coworkers, and data transfer security with partners/clients.

## **9.6 Methods for database locking at the start of analysis and storage upon completion of the clinical investigation**

The validated database will be locked upon request of the Data Manager following the completion of all steps required, i.e. resolution of all queries, validation of the coding, data review meeting.

## **9.7 Procedure for data retention**

Once the Clinical Investigation Report is signed and validated, the data are archived on a dedicated hard disk file with limited access rights. This specific file is mounted on AXIODIS's OVH server with a back-up every two months as well as copied to an external disk that will be stored under seal within the premises of AXIODIS. The data are conserved for at least 10 years.

## **10. Amendments to the CIP**

The investigator should not implement any changes of the protocol without agreement by the sponsor.

All changes to the protocol are subject to an amendment which must be dated and signed by the sponsor and the Principal Investigator and must appear as an amendment to the protocol.

Substantial amendments are notified to the EC and CA.

## **11. Deviation from Clinical Investigation Plan**

A major protocol violation is a deviation that has an impact on subject safety, may substantially alter risks to subjects, may have an effect on the integrity of the study data, or may affect the subject's willingness to participate in the study. In this PMCF study, the following deviations are considered major:

***Strictly Confidential***

- Non-compliance with the inclusion or exclusion criteria,
- No assessment of the primary efficacy criterion (WURSS-21) at D1, D4±1 and D8-1 during the treatment period,
- Intake of wrong treatment, i.e. wrong treatment given to the patient after randomization
- A compliance to study product intake below 80% or greater than 120%
- Intake of forbidden medication, i.e., nasal irrigation

All other cases will, a priori, be considered as minor deviations.

All protocol deviations will be managed as per the Standard Operating Procedures of the CRO.

A deviation log shall be maintained by the study site.

All deviations will be included, as required in the final study report.

Any major deviation from the protocol that has not been previously approved by the sponsor must be reported to the sponsor within 2 working days of the deviation occurrence. Any deviations from the clinical investigation plan that are identified during routine monitoring visits will be reported to the sponsor within 24 hours of being identified.

In case of major deviation, corrective and preventive actions will be implemented as per Study Deviation Management plan and Risk management plan.

## **12. Device accountability**

The device accountability will be performed all over the study according to the SOP “Investigational Product Management” of the CRO. Briefly, the site will complete an accountability log after each receipt of the Medical Device and delivery to subject. The CRA in charge of the site monitoring will check the accountability log at each visit. At V2, the accountability log will be completed with the weight of the returned device by the subject.

Return of unused or expired investigational devices to the sponsor will be tracked using a specific record.

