#### Visit 1 (V1) - (Day 1): Screening/Inclusion/Randomization

Subjects with symptoms of acute infectious rhinitis for  $\leq 48h$  will go to the site for the screening/inclusion visit (visit 1). The investigator will give oral information relative to the study and will answer all questions relative to the study participation. The patient will receive the information sheet. If the subject agrees to participate in the study, he/she will be asked to give a written consent.

Each screened subject will be assigned a subject identifier number during screening that will be used on all subject documentation. The subject identifier number will contain the site number and the subject number and will be assigned in numerical order at the screening visit based on chronological order of screening dates (e.g., 001-010 for the 10th subject screened at the Site #001).

The investigator or his/her delegated designee will:

- Record demographic data, medical history and ongoing medication.
- Perform a physical and clinical examination. A pharyngeal nasal swab will be performed by the investigator or by the delegated study nurse to check for absence or presence of SARS-CoV2.
- Verify that eligibility criteria are fulfilled.
- Record the score of the common cold symptoms (headache, muscle ache, chilliness, sore throat, blocked nose, runny nose, cough, sneezing according to a physician-rated symptom score after clinical examination; (scale: 0  $\rightarrow$  3 [0: no symptom, 1 = mild symptoms (sign/symptom clearly present, but minimal awareness; easily tolerated), 2 = moderate symptoms (definite awareness of sign/symptom that is bothersome but tolerable), 3 = severe symptoms (sign/symptom that is hard to tolerate; causes interference with activities of daily living and/or sleeping]). This scoring system was developed by Jackson in 1958 and is widely used in common cold clinical trials [14].
- Review and detail the question of the WURSS-21.
- Allocate a treatment number for eligible subjects via the eCRF.
- Explain how to complete every day the e-diary for WURSS-21 recording, how to report concomitant medications, adverse events/incidents/expected undesirable side effects. The patient will access the e-diary application using a smartphone.

*NB: The first WURSS-21 will be completed by the subject on site during this visit after the randomization of the patient.*

- Remind the patient to return the device for assessment of compliance to the treatment at V2.

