**D8 (Telephone Call):**

The investigator or his/her delegated designee will call the patient to remind him/her to stop the treatment.

➤ *NB: The last study nasal spray intake will be performed in the morning of the Day 8.*

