**Visit 2 (V2) – (Day 13-15): end of study**

The investigator or his/her delegated designee will:

- Perform a physical and clinical examination. A pharyngeal nasal swab will be performed by the investigator or by the delegated study nurse to check for absence or presence of SARS-CoV2.
- Validate adverse events pertinent in the context of the common cold and of additional study procedures /incidents linked to medical device use and concomitant medications reported in the e-diary and complete the e-CRF accordingly and report any new relevant safety events.
- Ask the patient to complete the WURSS-21 if he/she still has symptoms.
- Assessed the compliance to the treatment by weighting the device returned by the subject. In case of nasal spray dysfunction and attribution of a new treatment using the back-up randomization list, the compliance will be assessed by weighting both devices. If a nasal spray is lost, the investigator will ask the patient to specify the number of missed nasal spray use and will report the data into the e-CRF.
- Ask the patient to complete a satisfaction questionnaire.

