### 7.2. Protocol deviations

Protocol deviations will be discussed during the data review meeting and the status (minor or major) of these deviations will be validated in order to identify the subjects to be excluded from the Per-Protocol Set.

Major deviations are defined by:

- Non-compliance with the inclusion or exclusion criteria;
- No assessment of the primary efficacy criterion (WURSS-21) at D1, D4±1 and D8-1 during the treatment period;
- Intake of forbidden medication, i.e. local or systemic corticosteroids, non-steroidal anti-inflammatory drugs (NSAID) or saline nasal spray;
- Intake of wrong treatment, i.e. wrong treatment given to the patient after randomization;
- A compliance to study product intake below 80% or greater than 120%.

All other deviations will a priori be considered as minor, e.g.:

- Telephone call or V2's dates that do not conform with the flow chart of the study;
- Telephone call or V2 not performed;
- Daily phone call to the subjects (in case of WURSS-21 non-completion) not performed (between D1 and D8);
- Treatment stopped before or after D8 morning (less or more than 14 intakes of study product);
- Non-compliance regarding the informed consent form;
- WURSS data missing (but data available at D1, D4±1 and D8-1) until subject's recovery (two consecutive and negative – “not sick” – answers to the first item) or D15/subject's end of study, whichever occurs first.

Major and minor deviations and their types will be described by treatment group and overall. They will be summarised with frequencies and percentages. Subjects will be counted only once within each type of deviation and within each category (major/minor).

A listing of all deviations will be provided for all included subjects, including the category.

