## 9. COMPLIANCE

Compliance will be calculated according to the following formula and analysed on the Safety set, by treatment group and overall.

The compliance will be calculated as follows:

**Compliance (%) = [Initial weight of the container (g) – Real weight of the container at the end of the study (g)] × 100 / [Initial weight of the container (g) – Theoretical weight of the container at the end of complete study (g)]**

with:

- Initial weight of the container = 33g;
- Theoretical weight of the container at the end of complete study = 27.7g;

i.e.:

$$\text{Compliance} (\%) = \frac{(33 - \text{weight}_{\text{end}}) \times 100}{5.3}$$

with  $\text{weight}_{\text{end}}$  the real weight of the container at the end of the study in g.

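### Compliance rests on one bottle weight at V2, 5 to 7 days after the last scheduled intake, so any later spraying is counted as D1-D8 use and can decide Per-Protocol membership

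*Protocol*

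**What the plan says.** Protocol 7.4.1 fixes the end of treatment in its note on the D8 call: "The last study nasal spray intake will be performed in the morning of the Day 8". The bottle is not collected then. At V1 the site is told: "Remind the patient to return the device for assessment of compliance to the treatment at V2". Under "Visit 2 (V2) – (Day 13-15): end of study" the task is: "Assessed the compliance to the treatment by weighting the device returned by the subject". Protocol 12 agrees: "At V2, the accountability log will be completed with the weight of the returned device by the subject".

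SAP 9 takes a fixed starting weight of 33 g and a theoretical final weight of 27.7 g. Its only patient-level input is "the real weight of the container at the end of the study in g".

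Protocol 11 and SAP 7.2 both class as major "A compliance to study product intake below 80% or greater than 120" per cent, with no time window. SAP 5 removes patients with major deviations from the Per-Protocol (PP) set. That set serves the AUC of the total WURSS-21 score and of its two components, and SAP 6.4.7 computes all of these from D1 to D8.

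Among its examples of minor deviations, SAP 7.2 gives "Treatment stopped before or after D8 morning (less or more than 14 intakes of study product").

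On data capture, the D8 call is a reminder to stop (Protocol 7.4.1), and Protocol 8.6 gives its purpose as making sure treatment has ended after 14 intakes. Neither section mentions recording a count, a weight or a date. The diary content in Protocol 9.2 is WURSS-21, safety events and concomitant treatments. Missed uses are asked about only when a spray is lost (Protocol 7.4.1, V2).

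**The concern.** A weight loss measured once, at V2, gives the total drawn from the bottle but not when it was drawn. If a patient sprays after D8 morning, two opposite errors become possible. Someone who completed the scheduled course can be pushed above 120% and leave the PP set. Someone who under-used the spray during treatment can be lifted above 80% and stay in.

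The PP analyses concern D1-D8 only, yet behaviour after treatment would help decide who enters them. If patients who continue tend to be those recovering slowly, exclusion would be tied to the endpoint. That is plausible, but the documents contain no evidence on it.

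The minor deviation for stopping after D8 morning has the same gap. It needs to be known when use stopped, and the documents describe no field that captures this.

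**Working it through.** **Inputs.** Two puffs per nostril, twice daily for seven days, 14 intakes (Protocol 7.2.1). Puff volume 100 ± 20 µL (Protocol 3.7.1). Bottle 20 mL (Protocol 3.1.1). Weights 33 g and 27.7 g (SAP 9). Limits 80% and 120% (Protocol 11, SAP 7.2). V2 on D13-D15.

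**1. The plan's own figure.** 33 − 27.7 = 5.3 g, which reproduces the SAP 9 denominator.

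**2. Implied weights.** 14 intakes × 4 puffs = 56 puffs. 5.3 / 56 = 0.0946 g per puff; 5.3 / 14 = 0.379 g per intake.

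**3. Limits in grams and intakes.** 0.80 × 5.3 = 4.24 g, and 0.80 × 14 = 11.2, so 12 intakes in total are needed to reach 80%. 1.20 × 5.3 = 6.36 g, and 1.20 × 14 = 16.8, so the 17th intake passes 120%.

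**4. Time and volume available.** The gap is 13 − 8 = 5 to 15 − 8 = 7 days. At the same twice-daily rate, D8 evening to the evening before V2 allows 1 + 4 × 2 = 9 intakes (V2 on D13) to 1 + 6 × 2 = 13 (V2 on D15). The course uses 56 × 0.1 = 5.6 mL, leaving 20 − 5.6 = 14.4 mL. Thirteen more intakes would need 13 × 0.4 = 5.2 mL, so volume is no barrier.

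**5. The two misreadings**, at the SAP-implied weight per puff:

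| D1-D8 intakes | Later intakes | True D1-D8 use | Reading at V2 | Status |
|---|---|---|---|---|
| 14 | 3 | 14/14 = 100% | 17/14 = 121.4% | major, out of PP |
| 9 | 3 | 9/14 = 64.3% | 12/14 = 85.7% | within limits |

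**6. Sensitivity to pump output.** Reading = intakes × 4 × g per puff / 5.3. The density of 1 g/mL is an assumption; the documents give none.

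| g per puff | 14 intakes read | Later intakes to pass 120% after a full course | Total intakes to reach 80% |
|---|---|---|---|
| 0.080 | 84.5% | 6 | 14 |
| 0.0946 | 100% | 3 | 12 |
| 0.100 | 105.7% | 2 (16 intakes = 120.8%) | 11 |
| 0.120 | 126.8% | 0 | 9 |

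The direction of both errors is fixed, but the number of later intakes that triggers them is not. At 0.120 g per puff the scheduled course alone exceeds 120%, which is a separate source of error. The 9-plus-3 case also depends on pump output: 12 intakes at 0.080 g read 72.5%, below the limit.

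**The case against.** The strongest reply is that the plan has a safeguard. The D8 call tells the patient to stop, and the labels say seven days. A misreading needs someone to continue after that instruction. This stands as a limit on frequency. It does not close the gap, because the call is not described as recording anything.

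Second, a patient with 17 intakes of a 14-intake course has over-used the device, and catching that is what an upper limit is for. Minor for a small excess and major above 20% is a coherent grading. This also stands: such a patient is fully adherent only for D1-D8, and the two entries in SAP 7.2 do not contradict each other. What remains is that the set built on the limit serves D1-D8 analyses, while the limit also counts use outside that period.

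Third, deviation status is validated at a blinded review before lock (Protocol 9.3, SAP 7.2), where an odd reading can be discussed. True, but the documents describe nothing that would tell the meeting when the spray was used. The e-CRF pages and the call form are not in the documents, so an existing question cannot be ruled out.

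Fourth, pump tolerance can misclassify patients with no later use at all. That is correct, and the fix below does not cure it.

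A reader might go further in four ways that the documents do not support:
- That SAP 7.2 expects patients to continue. It only lists the category as an example.
- That a quarter of patients are still ill at D8. Protocol 4 says 75% have a reduction or resolution within 7 days; the rest lack even a reduction, so the share still ill is not given.
- That a number of lost PP patients can be derived. No rate of continuing is stated.
- That later use can never touch the AUC. The D8 questionnaire is completed in the evening, so a D8-evening spray can precede the last AUC point.

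**Conclusion.** The point holds as a measurement gap of limited reach. From the documents' own schedule and formula, the 80-120% rule can misread D1-D8 adherence in both directions. At the SAP-implied weight, three later intakes are enough for either error; at nominal pump volume, two take a completed course past the upper limit. The whole effect is conditional on spraying after D8 morning, and its frequency is unknown.

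It would be wrong to infer that the main result is at risk. The primary analysis is on the FAS, which does not use compliance. SAP 5 calls the PP analyses supportive, and SAP 6.3.1 treats only the primary criterion as conclusive. What is affected is the interpretation of the compliance table and the make-up of the PP set. Selection that differs by arm is possible in principle but not shown. This is a worthwhile improvement, not a condition for proceeding.

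**What to change.** - **Data.** At the D8 call, at V2, or both, record the date and time of last use and the number of intakes after D8 morning (k). V2 already allows a patient-reported count of missed uses when a spray is lost.
- **SAP 9.** Report D1-D8 compliance as (33 − final weight − k × 5.3/14) × 100 / 5.3, next to the unadjusted value. In the two cases above this returns 100% and 64.3%.
- **SAP 7.2.** For PP membership, apply the 80-120% limits to D1-D8 use and leave later use under the minor deviation already listed. Show PP membership under the unadjusted rule as a sensitivity check.

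The cost is one or two questions at existing contacts and a line in each SAP section. No visit, treatment instruction or primary analysis changes. The downsides are that the count relies on recall, and that error from pump tolerance and from the fixed 33 g starting weight remains.

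If data collection is already closed, the timing cannot be recovered from the weight. The table should then be labelled as total use up to V2, and the PP AUCs shown with and without patients excluded only for a reading above 120%.
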